3.10.2.7 Tipping point analysis

If the primary analysis is statistically significant in favor of GMRx2, a MI tipping point analysis may be performed in the Randomized Population to assess the impact of missing data under the assumption that data are not missing at random. A two-dimensional tipping point analysis will be performed where the trajectories of participants in the GMRx2 treatment groups with missing Week 4 data will be imputed separately from the trajectories from the placebo control treatment group with missing Week 4 data. A shift parameter, delta, will be added to each imputed value. The placebo control treatment groups will be imputed with a shift of 0. The shift parameter applied to the GMRx2 treatment groups will be applied across

a range of values. Successively larger deltas will be imposed on the imputed values of GMRx2 treatment group until statistical significance is lost, i.e. two-sided p-value is >0.05 and no longer in favor of GMRx2 for at least one of the pairwise comparisons.

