2.5 Sample Size

A total of 250 participants will be randomized: 100 for each of the GMRx2 doses and 50 for placebo group. As noted in Section 12.3 of the protocol, for the comparison of triple $\frac{1}{2}$ vs placebo at week 4, a sample size of 150 participants at a ratio of 2:1 will provide 99.7% power to detect a difference of at least 9 mmHg in mean home SBP, assuming a standard deviation of 11 mmHg. Similarly for the comparison of triple $\frac{1}{2}$ vs placebo at week 4, a sample size of 150 participants at a ratio of 2:1 will provide 100.0% power to detect a difference of at least 13 mmHg in mean home SBP, assuming a standard deviation of 11 mmHg. Therefore, the power for the two comparisons versus placebo will be 99.7% (since $0.997 \times 1.0 = 0.997$). Note that this is a simple, conservative sample size calculation by intention – the actual experimental design and subsequent statistical modelling approach will provide greater power than this.

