3.3 Multiplicity Adjustment

All tests are to be two-sided with a nominal level of α set at 5%. Since the purpose of the trial is to demonstrate effects on both of the GMRx2 dose versions versus placebo comparisons simultaneously for the designated primary endpoint (i.e., each GMRx2 dose has to be statistically significantly superior at two-sided $p<0.05$ to placebo for the trial to be regarded as positive), there is no need for adjustment of the Type I error for the primary endpoint, according to ICH E9 Guidance and FDA Guidance 'Multiple Endpoints in Clinical Trials. Guidance for Industry, 2022'.

The secondary efficacy parameters measure different aspects of the same underlying treatment effect evaluated in the primary efficacy endpoint, that is the effect of GMRx2 compared to placebo on blood pressure and do not demonstrate additional new treatment effects of the drug, but rather clarify the effect already demonstrated by the primary analysis. No type I error adjustment is proposed to adjust secondary efficacy endpoint analyses.

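### The tipping point analysis is labelled two-dimensional but holds the placebo shift at 0, so it never tests placebo dropouts with lower BP than imputed

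*SAP*

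**What the plan says.** SAP 3.10.2.7 opens conditionally: if the primary result favours GMRx2, "a MI tipping point analysis may be performed in the Randomized Population". The next sentence is firm: "A two-dimensional tipping point analysis will be performed where the trajectories of participants in the GMRx2 treatment groups with missing Week 4 data" are to be imputed separately from those on placebo. A shift is then added to each imputed value. For placebo the rule is "The placebo control treatment groups will be imputed with a shift of 0". For the active arms, "Successively larger deltas will be imposed on the imputed values of GMRx2 treatment group until statistical significance is lost", meaning that the "two-sided p-value is >0.05 and no longer in favor of GMRx2 for at least one of the pairwise comparisons". No range, step or plausibility limit for the shift is given. SAP 3.10.2.8 lists a graph of the results among the planned displays.

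The starting imputation is in SAP 3.10.2.6. Participants who discontinue for reasons related to treatment or study procedures (item 2b), and non-adherent participants (item 3), are imputed from placebo participants with intercurrent events. Adherent participants without an intercurrent event are imputed from similar participants in their own arm (item 4).

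**The concern.** A two-dimensional tipping point analysis moves the active and control shifts independently and maps where significance is lost. Imputing the arms separately does not create a second axis. With the placebo shift fixed there is one free parameter, and the label does not describe the method. No other section of the SAP shifts the placebo arm.

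The untested half of the grid corresponds to something the trial permits. Protocol 8.6 allows open-label add-on treatment for high BP, and Protocol 8.8 provides for alternative treatment after discontinuation. Under the treatment policy strategy in SAP 3.10.1.1, BP after such treatment counts. Add-on treatment is neither a listed intercurrent event nor one of the imputation factors in SAP 3.10.2.6. An adherent placebo participant who received add-on treatment and lacks a Week 4 home value is therefore imputed from all placebo participants without an intercurrent event, whether or not they had add-on treatment. If the imputed value is too high, the error favours GMRx2.

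At stake is the robustness statement for the primary endpoint. A report that followed this text would present a one-axis result as two-dimensional, without the scenarios that erode the contrast faster per mmHg of shift in each arm.

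**Working it through.** **Inputs from the documents.** SD 11 mmHg; effects of 9 mmHg (triple ¼) and 13 mmHg (triple ½) versus placebo (Protocol 12.3, SAP 2.5; SAP 2.5 prints triple ½ for both comparisons); 100 per GMRx2 arm and 50 on placebo; two-sided 5% (SAP 3.3).

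**Assumption.** Neither document gives the proportion with missing Week 4 home SBP. A range of 0 to 20% is used, equal and unequal between arms.

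**The plan's own figure.** SE = 11 × √(1/100 + 1/50) = 1.905. For 9 mmHg, 9/1.905 = 4.72 and 4.72 − 1.96 = 2.76, which gives power of 99.7%. This agrees with the SAP statement that the design "will provide 99.7% power to detect a difference of at least 9 mmHg in mean home SBP, assuming a standard deviation of 11 mmHg". For 13 mmHg power exceeds 99.99%, matching the stated 100.0%. The documents state no tipping-point figure.

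**Margin.** Significance is lost once the estimated effect falls to 1.96 × 1.905 = 3.73 mmHg, so the margin at 9 mmHg is 9 − 3.73 = 5.27 mmHg.

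**Tipping shift.** Move imputed GMRx2 values by +x and imputed placebo values by −k·x. With missing proportions mA (GMRx2) and mP (placebo), the shifted effect is d − mA·x − k·mP·x. Setting k = 0 gives the SAP rule; k = 1 gives equal and opposite shifts.

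- Fixed SE: x = 5.27/mA for k = 0 and x = 5.27/(mA + mP) for k = 1. The ratio is (mA + mP)/mA = 1 + mP/mA.
- Allowing for the spread that the shift itself adds: the arm variances become 121 + mA(1 − mA)x² and 121 + mP(1 − mP)(kx)², and x solves d − mA·x − k·mP·x = 1.96 × √(varA/100 + varP/50).

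Check at 10% missing in both arms, k = 0, x = 44.4: varA = 121 + 0.09 × 44.4² = 298.4; SE = √(2.984 + 2.42) = 2.325; 1.96 × SE = 4.56; shifted effect = 9 − 4.44 = 4.56.

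**Results, d = 9, 100 versus 50 (mmHg):**

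| Missing GMRx2 / placebo | Fixed SE: one-axis, opposite, ratio | With added variance: one-axis, opposite, ratio |
|---|---|---|
| 5% / 5% | 105.3, 52.7, 2.0 | 79.2, 41.6, 1.90 |
| 10% / 10% | 52.7, 26.3, 2.0 | 44.4, 23.0, 1.93 |
| 20% / 20% | 26.3, 13.2, 2.0 | 24.1, 12.3, 1.96 |
| 10% / 2% | 52.7, 43.9, 1.2 | 44.4, 37.0, 1.20 |
| 5% / 10% | 105.3, 35.1, 3.0 | 79.2, 29.2, 2.72 |
| 5% / 15% | 105.3, 26.3, 4.0 | 79.2, 22.7, 3.49 |
| 10% / 0% | 52.7, 52.7, 1.0 | 44.4, 44.4, 1.0 |

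A small multiple-imputation simulation combined by Rubin's rules agrees: 42.6 versus 22.3 at 10%/10% (1.91), 22.3 versus 11.6 at 20%/20% (1.92), and 44.2 versus 36.6 at 10%/2% (1.21).

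**Other inputs.** For 13 mmHg the added-variance figures are 73.1 versus 38.1 at 10%/10% and 40.5 versus 20.8 at 20%/20%. For the 295 randomized (SAP 2.6.1), taken as 118:118:59 if allocation was exactly 2:2:1, the 9 mmHg figures are 47.2 versus 24.4 and 25.5 versus 13.0. The ratios barely change.

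These calculations use a simple two-arm comparison with own-arm imputation. Baseline adjustment, site clustering and the control-based part of the imputation are left out.

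**The case against.** The strongest reply is that a delta adjustment of the active arm with placebo held at 0 is a recognised method, and that halving the per-arm shift partly reflects how the shift is counted. With equal missingness and a fixed SE, +52.7 mmHg in GMRx2 alone and 26.3 mmHg in each arm in opposite directions are the same total departure. That is correct. In terms of the total differential, the one-axis rule is not lenient when missingness is equal, and it is the harsher one when placebo loses fewer participants (10%/2%: 44.4 against 37.0 + 37.0 = 74.0). It is lenient when placebo loses more (5%/15%: 79.2 against 22.7 + 22.7 = 45.4). Which case applies cannot be read from the documents, and a grid would show it.

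A reader might infer that this is the plan's only check on data missing not at random. The documents do not support that. Items 2b and 3 of SAP 3.10.2.6 already depart from missing at random, and the clinic BP substitution analysis (SAP 3.10.1.1) uses observed clinic values in place of missing home values in every arm. Neither applies a shift to placebo, so the gap remains, but it is narrower than that inference suggests.

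The placebo mechanism is also partly handled. Add-on treatment does not require stopping trial medication, participants who discontinue are to complete all visits (Protocol 8.8), and a single valid reading in the 7 days yields an endpoint (SAP Table 3-2). With a 4-week treatment period and telemonitored home BP, missingness may well be below 10%.

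Finally, a reader might call the analysis optional. The text is inconsistent rather than plainly optional: SAP 3.10.2.7 uses both permissive and firm wording, and SAP 3.10.2.8 plans the graph.

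**Conclusion.** The point holds as a mismatch between label and method that leaves one set of scenarios untested. The rule as written is one-dimensional, and this is the only delta-shift sensitivity analysis planned. Per mmHg of shift in each arm, its tipping point exceeds the equal-and-opposite one by about 1 + mP/mA.

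It is tempting to conclude that the plan makes the result look twice as robust. That needs equal missingness and equal-and-opposite shifts, neither of which the documents give. The factor is 1 with no missing placebo data and about 3.5 at 5%/15%.

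Nor do the figures suggest that the primary conclusion is in danger. At the smaller design effect with 20% missing in both arms, missing participants would have to be about 12 mmHg worse on GMRx2 and about 12 mmHg better on placebo than imputed. For scale, the assumed SD is 11 mmHg, and Protocol 5.7 credits standard-dose monotherapy with 8–9 mmHg. The conclusion would probably survive unless the effect were smaller or missingness higher. The text is certain; the size rests on assumed missingness. The correction is worth making because it is cheap and determines what the report may claim about robustness.

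**What to change.** In SAP 3.10.2.7, pre-specify a grid of shifts applied separately to each GMRx2 arm (from 0 upward) and to placebo (including negative values), with the range and step stated. Report the p-value over the grid, or the tipping boundary, for each dose separately, instead of stopping when the first comparison loses significance. Reconcile the permissive and firm wording by committing to the analysis whenever the primary result is significant. If the sponsor prefers to keep placebo at 0, the minimum change is to call the analysis one-dimensional and state that lower-than-imputed placebo values are not examined.

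The cost is a change of SAP wording and one extra loop in the existing code. The downside is a robustness statement that may look less favourable.

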3.10.2.8 Descriptive figures

The following graphical displays are planned:

- Plot of the LS Mean home SBP with 95% CI derived from the MM for the primary analysis will be presented.
- Results from the tipping point analysis will be presented graphically.
- Forest plots of the LS Means, 95%CI and p-values for determining heterogeneity by subgroup will be presented.
- Descriptive plots to display the average weekly SBP post-randomization, where Week 1 begins at first treatment post-randomization, Week 2 begins at Day 8 of treatment post-randomization, etc.
- Descriptive plots to display the change in average weekly SBP from randomization through the Randomization Period. Randomization will be defined as the 7 calendar days prior to the Randomization clinic visit (Table 3-2). The Randomization Period will begin on the first day of randomized treatment and will extend until the earliest of: FU1/Week 4 visit, End of Study visit, or 7 weeks of post-randomized BP home measurements.

Plots may be presented for the treatment groups overall as well as by subgroups, as appropriate. Similar plots may be presented for home DBP, as appropriate.

3.10.3 Analysis of Secondary Efficacy Endpoints

3.10.3.1 Home Blood Pressure

Analysis of home SBP and DBP secondary continuous endpoint analysis on change from baseline (randomization) will be performed on Complete Cases only, including all data available. Summary statistics, including number with missing observations, at each timepoint will be presented. MMRM will be applied for continuous variables using the same approach as the primary endpoint (with no imputations applied).

- Difference in change in mean home DBP from baseline to Week 4,
- Difference in change in trough home mean SBP from baseline to Week 4,
- Difference in change in trough home mean DBP from baseline to Week 4.

Additional exploratory analyses, including longitudinal models for all home SBP measurements collected through Week 4, may be performed.

Descriptive summaries of binary endpoints will include the number and percentage of participants with controlled BP, i.e.:

- Weekly averaged home SBP <135 and DBP <85 mmHg at Week 4,
- Weekly averaged SBP <130 and DBP <80 mmHg at Week 4

Frequency of missing data will be reported. Data will be summarized as reported, including only complete cases. Estimated proportions by treatment groups with exact Clopper-Pearson 95% CI will be presented along with the associated estimated risk difference, risk ratio and corresponding p-values. The number and percentage with 95% CI of participants with controlled BP at Week 4 will be summarized by treatment group by:

- Number of prior therapies at enrolment
- Controlled or uncontrolled BP status at Screening

Binary secondary endpoints will also be analyzed using Generalized Estimating Equations (GEE) to account for clustering at the site level. For the regression analysis, participants with missing endpoint data (Week 4) will be imputed as "failure". The GEE regression analyses will be performed on the Randomized Set. The

endpoint will be the post-Baseline occurrence of the event at Week 4 with fixed effects for treatment group and Baseline home SBP. The variance will be estimated using a sandwich estimator and the model will account for correlation within site. A compound symmetry covariance matrix will account for correlation within site with a fall back of an independent matrix if the model does not converge. The odds ratios and 95% confidence intervals for the occurrence of the events will be estimated for each post-Baseline visit and treatment group. In addition, risk differences and 95% CI will be computed. Pairwise comparisons between GMRx2 doses and placebo will be performed.

Sample SAS Code:

```
PROC GENMOD DATA = ADEFF;
  CLASS SITEID TRTP;
  MODEL AVAL = BASE TRTP / DIST = BIN CL;
  REPEATED / SUBJECT = SITEID TYPE = EXCH;
  WHERE VISIT IN ('WEEK4');
  LSMEANS TRTP / DIFF CL ALPHA=0.05;
  RUN;
```

Risk differences and 95%CI for comparisons between the occurrence of events in GMRx2 dose levels versus Placebo will be computed using the Predictive Margins and Average Marginal Effects SAS Macro (<https://support.sas.com/kb/63/038.html>). Risk differences and 95%CI between GMRx2 dose levels will also be computed. Sample SAS code with implementation to simulated data is provided in Appendix 3.

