10. PARTICIPANT TIMELINE & ASSESSMENTS

10.1. Schedule of Evaluations

Table 5 outlines the trial visits schedule and assessments for participants in the trial who do not enter the optional Open-Label extension period; for those who do enter the Open-Label Extension period, **Table 6** outlines the visits schedule from Week 4 onwards. It should be noted that there is flexibility in the timing of blood and urine collection tests before randomization as noted in **Table 5**, to suit participant preferences and local clinic feasibility and ease of scheduling, with the proviso that all of the requirements for eligibility at Screening and Randomization are met, as outlined in Section 8.2.

Table 5: Trial visits schedule and assessments: Randomization and Safety Follow-up Periods

Visit Name	PRE-SCREEN (Optional)	SCREEN (Run-in start)	RAND (Run-in end)	FU1 (End of trial medication)	EOT ⁵ (Telephone safety FU)
Visit Week	Week -4	Week -2		Week 4	Week 8
Visit Day (Visit window days)	-28	-14 (-12 to -21)*		28 (±7)*	56 (±7)*
Written informed consent ¹	✓	✓			
Eligibility (inclusion & exclusion)	✓	✓	✓		
Medical history	✓	✓			
Physical examination ²		✓			
Demographics		✓			
Anthropometrics – Height, weight		✓			
Clinic BP, standing BP, pulse		✓	✓	✓	
12-lead electrocardiogram (ECG)		✓			
Cardiovascular risk assessment		✓			
Dispensing of home BP monitor		✓			
Home BP monitoring				→	
Home BP monitor brought to clinic			✓	✓	
24-hour ambulatory BP measurement if participating in substudy				✓	
Blood Collection					
Study bloods ³		✓		✓	
Follow-up creatinine with eGFR ⁴					✓ ⁴
Pregnancy test if childbearing potential		✓			
Blood sample for storage for substudy		✓		✓	
Urine Collection³					
Albumin-creatinine ratio		✓		✓	✓ ⁴
Urine sample for storage for substudy		✓		✓	✓ ⁴
Medications					
Discontinue BP lowering medication (if applicable)	✓	✓			
Dispensation of run-in medication		✓			
Allocation of randomized trial medication			✓		
Dispensation of trial medication			✓		
Return of trial medication			✓	✓	
Adherence to trial medication			✓	✓	
Review of concomitant medications	✓	✓	✓	✓	✓
Safety					
AESI or SAE					→

¹ At Screening visit, if not collected previously. Written informed consent may be collected at pre-screening.

² Systems-based examination deemed necessary for the safety of participants by the site investigator

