3.5.2 Baseline Definitions

For Period 1, Baseline for safety and in-clinic assessments is defined as the most recent measurement prior to the first administration of placebo run-in study treatment.

For in-clinic efficacy parameters, including change from baseline measurements at post-Randomization timepoints, Baseline is the last Clinic BP measurement occurring prior to the first dose with randomized

study treatment.

Baseline for home SBP measurements is defined as measures taken during the week prior to Randomization, with derivation defined in [Table 3-2](#).

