3.10.3.2 In Clinic Blood Pressure

At each scheduled trial visit, triplicate BP measurements will be performed “in clinic” after 5 minutes of seated rest and with a 1-minute interval between measurements. The last two measurements will be averaged. If only two measures were taken, both will be averaged and if only 1 measure is taken that value will be used.

The baseline value for clinic BP measurement is the value recorded at Week 0. Standing clinic BP measurements will also be summarised descriptively.

Analysis

In clinic BP endpoints listed below:

- Difference in change in clinic SBP from baseline to Week 4,
- Difference in change in clinic DBP from baseline to Week 4,
- Percentage of participants with clinic SBP <140 and DBP <90 mmHg at Week 4,
- Percentage of participants with clinic SBP <130 and DBP <80 mmHg at Week 4
- Percentage of participants with orthostatic hypotension at Week 4
- Percentage of participants with orthostatic hypertension at Week 4

Orthostatic hypotension is defined as a decrease from measured in clinic sitting to standing blood pressure of ≥ 20 mmHg SBP or ≥ 10 mmHg DBP. Orthostatic hypertension is defined as an increase from measured in clinic sitting to standing blood pressure of ≥ 20 mmHg SBP or ≥ 10 mmHg DBP.

Descriptive statistics will be used to summarize secondary endpoints on complete cases only. Continuous endpoints will be summarized using descriptive statistics. Binary endpoints will be summarized with frequency and proportions by treatment groups with exact Clopper Pearson 95% Cis along with associated estimated risk difference, risk ratio and corresponding p-values. Frequency of missing data will be presented. Comparisons will be made between GMRx2 dose levels and Placebo. Exploratory comparisons between GMRx2 dose levels will also be computed.

MMRM will be applied for continuous endpoints using the same approach as the primary endpoint (with no imputations applied). Results will be presented in a similar fashion as home BP. Standing clinic BP measurements will be summarised descriptively by visit. Complete cases analysis will be performed with no imputations for continuous endpoints.

Binary secondary endpoints will be analyzed using GEE regression methods in the same manner as home BP endpoints. Risk differences and 95% CI will be computed for comparisons between GMRx2 dose levels and placebo. Missing values at Week 4 will be imputed as “failures” for the analysis.

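### Read literally, the model for clinic BP control adjusts for baseline home SBP; naming baseline clinic SBP and DBP instead would gain some precision at almost no cost

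*SAP*

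**What the plan says.** SAP 3.10.3.1 introduces the GEE for binary secondary endpoints and gives it "fixed effects for treatment group and Baseline home SBP". No other baseline term is named, and no DBP term appears. The sample code below it reads "MODEL AVAL = BASE TRTP / DIST = BIN CL"; the section does not tie `BASE` to home or clinic BP.

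SAP 3.10.3.2 lists two clinic control endpoints: "Percentage of participants with clinic SBP <140 and DBP <90 mmHg at Week 4" and "Percentage of participants with clinic SBP <130 and DBP <80 mmHg at Week 4". On the model it says: "Binary secondary endpoints will be analyzed using GEE regression methods in the same manner as home BP endpoints". It names no different covariate.

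The SAP does define a clinic baseline. Section 3.5.2 states, for in-clinic efficacy parameters, that "Baseline is the last Clinic BP measurement occurring prior to the first dose with randomized" study treatment, and 3.10.3.2 adds "The baseline value for clinic BP measurement is the value recorded at Week 0". The schedule in Protocol 10.1 has a row "Clinic BP, standing BP, pulse" that is ticked at screening, randomization and Week 4.

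Three other provisions matter:

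- Protocol 8.2.1 requires a mean home SBP of 130–154 mmHg for randomization.
- SAP 3.10.1.2 plans no hypothesis testing for secondary endpoints and calls their results exploratory.
- The sample macro call in SAP Appendix 3, which illustrates the risk difference on simulated data, has treatment as its only model term and clusters on the simulated subject index.

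**The concern.** A covariate improves precision to the extent that it predicts the outcome. For clinic control at Week 4, the same measurement at randomization is the natural candidate, and both endpoints need SBP and DBP to be below a limit. The literal model instead uses a different measurement, SBP only, whose range has been narrowed by the entry criterion. That would forgo precision that is already paid for, in a comparison with a small placebo arm (50 planned).

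There is also a reporting issue. The SAP reports both odds ratios and risk differences. An odds ratio from a logistic model depends on which covariates are conditioned on. If text, code and macro call are followed as they stand, the odds ratio might be adjusted for home SBP or clinic SBP, while the risk difference is unadjusted. The choice should be fixed before unblinding.

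**Working it through.** **The plan's own figure.** SAP 2.5 states 99.7% power for 9 mmHg in home SBP, SD 11 mmHg, 100 versus 50, two-sided 5%.

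SE = 11 × √(1/100 + 1/50) = 1.905; 9/1.905 = 4.724; power = Φ(4.724 − 1.96) = 0.9971.

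The figure reproduces (0.9969 by noncentral t). It concerns the primary endpoint and is unaffected by this point. No power is stated for clinic control.

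**Simulation.** No closed form applies, and the documents give no home–clinic or clinic–clinic correlation, so the rest is illustrative.

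- From the documents: 100 versus 50, the two pairs of cut-offs, two-sided 5%. The 9 mmHg is the planned home SBP effect, assumed here to hold for clinic SBP.
- Assumed: clinic mean 140/87 mmHg, SD 14/9, DBP effect 5 mmHg, SBP–DBP correlation 0.6, and the correlations in the table. Home SBP was not truncated explicitly; its lower correlations stand in for the restriction.
- Method: 2,000 runs per row, logistic model, risk difference by standardization, no site clustering. Power is for the Wald test of the odds ratio.

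Correlations are, in order: baseline clinic with Week 4 clinic; baseline home with Week 4 clinic; baseline home with baseline clinic.

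| Endpoint | Correlations | SE of risk difference, home SBP | SE, clinic SBP + DBP | Ratio | Power, home → clinic |
|---|---|---|---|---|---|
| below 140/90 | 0.5, 0.25, 0.4 | 0.0811 | 0.0761 | 0.939 | 86.2% → 89.9% |
| | 0.5, 0.4, 0.5 | 0.0813 | 0.0775 | 0.953 | 87.7% → 89.4% |
| | 0.5, 0.5, 0.5 | 0.0805 | 0.0797 | 0.990 | 87.3% → 88.7% |
| | 0.6, 0.3, 0.4 | 0.0821 | 0.0752 | 0.916 | 85.0% → 92.2% |
| | 0.6, 0.4, 0.5 | 0.0810 | 0.0743 | 0.918 | 87.5% → 92.0% |
| | 0.6, 0.5, 0.6 | 0.0801 | 0.0768 | 0.959 | 88.6% → 91.1% |
| | 0.7, 0.3, 0.4 | 0.0799 | 0.0694 | 0.869 | 87.1% → 94.7% |
| | 0.7, 0.5, 0.6 | 0.0792 | 0.0708 | 0.895 | 87.5% → 94.2% |
| below 130/80 | 0.6, 0.3, 0.4 | 0.0648 | 0.0607 | 0.936 | 69.6% → 77.9% |
| | 0.6, 0.5, 0.6 | 0.0613 | 0.0587 | 0.958 | 73.2% → 78.8% |

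**Reading the table.**

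- The SE falls by 1–13% for 140/90 and by 4–6% for 130/80. In sample-size terms (1/ratio²) the extremes for 140/90 are 1/0.990² = 1.02 and 1/0.869² = 1.32.
- The mean risk difference stays at about 0.25 (140/90) and 0.18 (130/80) with either covariate set.
- Adjusting for home SBP lowers the SE by only about 1–7% compared with no covariate.
- The power gain at 100 versus 50 is 1.4–7.6 points for 140/90 and 5.6–8.3 points for 130/80.
- The conditional odds ratio moves. In the row 0.6, 0.3, 0.4 for 140/90, the median log odds ratio goes from 1.11 to 1.37, that is, from e^1.11 = 3.0 to e^1.37 = 3.9. This is non-collapsibility: the target changes, and no error is being corrected.

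**At the size actually randomized.** SAP 2.6.1 reports 295 randomized, which at 2:2:1 is about 118 versus 59. Runs at that size, again with SBP and DBP cut-offs and assumed correlations, gave an SE 4–13% smaller and a power gain of about 1–5 points at 9 mmHg and 2–10 points at 6 mmHg. The 1–5 range is not a ceiling: the gain is larger where power is lower, as the 130/80 rows show.

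**The case against.** **The literal reading may not be the intended one.** The home SBP term stands in a section on home BP, the code uses a generic `BASE`, and a clinic baseline is defined twice, once within the clinic section itself. SAP 3.10.3.2 also sends the continuous clinic endpoints to the primary model, whose stated covariate is home SBP; taken equally literally, clinic DBP change would be adjusted for home SBP. The same method with each endpoint's own baseline is a natural reading. SAP 2.1 also says that sample code may need modification, and the Appendix 3 example has no baseline variable to adjust for. All of this stands. A reader might infer that the SAP commits to a wrong model; the documents show only that the one covariate named in the text is home SBP and that nothing settles the matter.

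**The size is unproven.** A reader might infer that the clinic baseline predicts clinic control far better. That is plausible, but no figure in the documents supports it, and with equal correlations (0.5 and 0.5) the SE gain is 1%. Clinic BP is also restricted at entry: 160/100 mmHg or above is excluded at screening and re-checked at randomization, although there is no window like the one for home SBP. A gain near 10 points belongs to a 6 mmHg effect, below the planned 9 and 13 mmHg. At 13 mmHg, runs with the SBP cut-off alone gave about 99.5% power or more with either covariate.

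**Power has limited relevance, and there is no bias.** The endpoints are exploratory, and unadjusted proportions, risk differences and risk ratios are reported too. Against that, the Protocol synopsis lists BP control among the key secondary efficacy outcomes, and p-values are planned. A reader might infer that chance imbalance in clinic BP would bias the comparison; randomization rules that out, and the standard error already allows for such imbalance.

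**Conclusion.** The point holds as an improvement in precision and clarity. On the literal text, clinic BP control is adjusted for baseline home SBP, no clinic or diastolic baseline is named, and text, code and macro call do not agree on a model. Using clinic SBP and DBP would lower the standard error of the risk difference by roughly 1–13%, leave its mean unchanged, and change the conditional odds ratio. Everything about size rests on assumed correlations, means and SDs, and on simulations without site clustering. The primary analysis is untouched and no success criterion depends on these models, so severity is low.

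**What to change.** In SAP 3.10.3.2, name baseline clinic SBP and baseline clinic DBP as the covariates for both clinic control endpoints, and state one definition of the clinic baseline. In 3.10.3.1, state what `BASE` stands for in each model. Use the same covariates in the text, the GENMOD code and the marginal risk-difference call, so that odds ratio and risk difference come from one model, and have that call cluster on site as the GEE does. For the home control endpoints home SBP is already a matching baseline; adding baseline home DBP is optional, and its gain was not computed.

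The cost is a few lines of SAP text and code, settled before unblinding. The measurements are already scheduled, so no new data are needed.
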